Adolescents with intellectual and developmental disabilities (IDD) are less physically active and have lower cardiovascular fitness compared with their typically developing peers. Similar to their typically developing peers, low moderate-to-vigorous physical activity (MVPA) and low cardiovascular fitness are associated with increased chronic disease risk and decreased quality of life in this group. Adolescents with IDD also face additional barriers to participation in MVPA including dependence on parents for transportation to exercise facilities, lack of appropriate exercise facilities, lack of professionals with expertise regarding their specific needs, and lack of peer support. The limited number of trials that have evaluated strategies to increase MVPA in adolescents with IDD were generally short-term (8-24 wks.), non-randomized, and were conducted in small samples ($n \leq 30$), at a gym, community center or other type of facility, and were generally unsuccessful in increasing MVPA. Data from our group, and others, suggest that the time and expense required for parents to transport their adolescents to a facility represents a major barrier to participation in PA. This suggests that alternative strategies for delivery of PA interventions for adolescents with IDD, which eliminate the transportation barrier, need to be developed and evaluated. Results from our single arm, short-term (12 wks.) pilot trial ($n = 29$) suggest the feasibility of delivering an intervention to increase MVPA in adolescents with IDD via video conferencing. In our pilot, health coaches delivered three 30-min. real-time MVPA sessions/wk. via video conferencing on an iPad (Zoom software), to groups of 5-6 adolescents with IDD in their homes. Participants were asked to complete additional MVPA between scheduled group sessions. Participants attended 77% of possible sessions, with an average heart rate of ~124 beats/min. This approach promoted interactions between both the group leader and participants (24/session), and between individual participants (12/session), and a 25% increase from baseline in objectively assessed daily PA (Garmin Vivofit). However, the effectiveness of the group video approach, or the effect of including parental education/support to increase and maintain MVPA over a longer time-frame (12-18 mos.) in adolescents with IDD is unknown. Parental involvement may be important in increasing MVPA in adolescents with IDD, who by the nature of their condition are more dependent on parents than typically developing adolescents. Thus, as requested by PAR-14-315, we propose to compare the effect of two strategies to increase MVPA in adolescents with IDD; a single level intervention delivered to the adolescent only, and a multi-level intervention delivered to both the adolescent and a parent. We propose an 18 mo. trial (6 mos. active, 6 mos. maintenance, 6 mos. no-contact follow-up) using intent-to-treat principles to compare changes in objectively assessed MVPA in 114 adolescents with IDD randomized to a single level intervention delivered to the adolescent only (AO) or a multi-level intervention delivered to both the adolescent and a parent (A+P). Adolescents in both intervention arms will be asked to attend three 40-min., home-based, group MVPA sessions/wk. (0-6 mos.) and one 40-min. sessions/wk. during mos. 7-12. A trained health coach will conduct group exercise sessions using video conferencing software (Zoom™ Video Conferencing Inc., San Jose, CA). Adolescents will be asked to complete a weekly activity homework assignment to reach a target of 300 min. of MVPA/wk. Parents of adolescents in the AO group will receive a reminder phone call if the adolescent misses more than two consecutive scheduled MVPA sessions. Parents of adolescents in the A+P group will be asked to participate in the group video MVPA sessions, attend educational/support sessions with their adolescent and the health coach regarding the role of MVPA in health and function and support their adolescent in completing their activity homework assignments. Education/support sessions will include strategies for increasing MVPA in both the adolescent and parent (0-6 mos. 2 session/mo.; 7-12 mos. 1 session/mo.).

Primary aim: To compare changes in MVPA (min./d) between the AO and A+P groups across 6 mos. We expect a significantly greater increases in MVPA in adolescents in the A+P vs. the AO group.

Secondary aims: To compare changes between the AO and A+P groups on the following variables across 18 mos.: 1) MVPA (min/d) and sedentary time (adolescents and parents). Adolescents only: 2) cardiovascular fitness, 3) muscular strength, 4) motor ability, 5) quality of life. We will also compare the percentage of adolescents achieving an average of 60 min/d of MVPA (US recommendation) across 18 mos. We expect more favorable changes for all secondary outcomes in adolescents in the A+P vs. the AO group.

Exploratory aims. To examine the influence of the following process variables/participant characteristics to identify salient factors impacting change in MVPA across 18 mos.: attendance at group video (AO-adolescent; A+P-adolescent/parent) and education/support sessions (A+P only), self-monitoring of PA (AO-adolescent; A+P-adolescent/parent), parental use of Facebook page (A+P only), peer interactions/support during group PA sessions, adolescent self-efficacy, social support and barriers for PA, parental MVPA, parental beliefs and attitudes toward PA, and parental time constraints, adolescent age, sex and IDD diagnosis.

Rationale

Approximately 1-3% of the US population is diagnosed with an intellectual or developmental disability (IDD) defined as a disability originating before the age of 10, characterized by significant limitations in both intellectual functioning ($IQ < 75$) and limitations in 2 or more adaptive behaviors ¹. Both typically developing adolescents and adolescents with IDD have low levels of moderate-to-vigorous physical activity (MVPA) ^{2,3}. However, compared to their typically developing peers, adolescents with IDD have even lower daily MVPA ³. Phillips and Holland reported no adolescents with IDD achieved the recommended 60 min. of daily MVPA ⁴. In a previous trial by our group, MVPA, assessed by accelerometer of adolescents with IDD ($n=20$), was only 23 min./d ⁵. Low MVPA is associated with reduced cardiovascular fitness ^{6,7}, reduced muscular strength and endurance ^{8,9}, and high prevalence of overweight and obesity in adolescents with IDD ^{10,11}.

Several trials have evaluated the impact of exercise training on cardiovascular fitness and chronic disease risk factors in individuals with IDD ¹²⁻¹⁴. However, few interventions have been designed specifically to evaluate strategies to improve PA in adolescents with IDD. A 2019 review identified only five PA trials in adolescents with IDD, most of which were unsuccessful ¹⁵. Thus, there is a need to develop and evaluate effective intervention to increase PA in adolescents with IDD.

Interventions targeting interpersonal factors, e.g., parental or caregiver education/support, can shape the PA behavior of adolescents through direct modeling, providing support and positive reinforcement, enforcing household rules that encourage or discourage PA, and creating a home environment supportive of PA ^{16,17}. In typically developing children/adolescents, interventions to increase PA by targeting parenting practices have been minimally effective ^{18,19}. However, adolescents with IDD are more dependent on their parents than typically developing adolescents. Thus, interventions that include a parent component may be effective for increasing PA in this group. Several cross-sectional studies have shown an association between greater parental support and higher parent/caregiver proxy reported PA in adolescents with IDD ²⁰⁻²². Curtin et al. ²³ randomized overweight adolescents with Down syndrome (DS) to a 6-mo. intervention designed to improve nutrition and MVPA with ($n=11$) or without parental training/support ($n=10$). On average MVPA (accelerometer) increased 18 min./d ($p=0.01$) with parental training/support and decreased 7 min./d ($p=0.30$) without parental training/support. However, Hinckson et al. ²⁴ reported no change in PA assessed by parent self-report in a 10-wk. school-based, single-arm trial in 22 adolescents with IDD that included a family educational component.

The limited information available and the potential health benefits of increased MVPA highlight the need to evaluate the effectiveness of multi-component interventions targeting both intra (adolescent) and interpersonal levels (parents and peers) to promote increased MVPA in adolescents with IDD.

Research Plan and Design

Overview of study design (Table 1)

One hundred fourteen adolescents with mild to moderate IDD and one of their parents will be randomized to an 18-mo. trial with 6 mos. active intervention period, a 6 mos. maintenance period, and a 6 mos. no-contact follow-up to compare changes in objectively assessed MVPA (ActiGraph LLC, Pensacola, FL) in adolescents with IDD randomized to a single level intervention delivered to the adolescent only (AO), or a multi-level intervention delivered to both the adolescent and a parent (A+P). Adolescents in both intervention groups will be asked to attend three 40-min., home-based, group MVPA sessions/wk. (5-7 adolescents, 0-6 mos.) and one 40-min. education/support session/wk. during mos. 7-12. Group sessions will be conducted by a trained health coach using video conferencing software (ZoomTM Video Conferencing Inc., San Jose, CA). Adolescents will be asked to complete a weekly activity homework assignment that in conjunction with the remote sessions will help them achieve a target of 300 min. of MVPA/wk. Parents of adolescents in the AO group will receive a reminder phone call if the adolescent misses more than 3 consecutive scheduled sessions. Parents of adolescents in the A+P group will be asked to participate in the group video MVPA sessions and homework activity, and to attend education/support sessions with their adolescent and health coach. These sessions will inform parents regarding the role of MVPA in health and function and provide strategies for increasing MVPA in both their adolescent and themselves.

Table 1. Design Overview for the Active 18-Month Weight Management Intervention

Interventions Groups	
Adolescent Only (AO)	Adolescent + Parent (A+P)

MVPA recommendation	60 min/d	60 min/d
MVPA group sessions via video conferencing	Yes	Yes
Session Participants	Adolescent Only	Adolescent + Parent
Session frequency		
0-6 mos.	3 d/wk.	3 d/wk.
7-12 mos.	1 d/wk.	1 d/wk.
13-18 mos.	0 d/wk.	0 d/wk.
Session intensity	≥ 4 METs	≥ 4 METs
Session duration	40 min	40 min
Session content	Stretch/aerobic activity/RE	Stretch/aerobic activity/RE
Provide access to PA resources	Yes	Yes
MVPA Self-monitoring	Fitbit	Fitbit
Parent contacts		
Participants	NA	Parent + Adolescent
Purpose	NA	Education/support/feedback
Format	NA	FaceTime™
Session Frequency		
0-6 mos.	NA	1 d/mo.
7-12 mos.	NA	1 d/mo.
13-18 mos.	NA	0 d/mo.
Duration	NA	30 min
Parent Facebook group	NA	Yes

Note: MVPA= Moderate-to-Vigorous Physical Activity, RE= resistance exercise

Participant eligibility.

Primary care physician (PCP) clearance will be required for both adolescents and the participating parent. To enhance generalizability, adolescents with congenital heart disease, or other chronic diseases, will be allowed to participate with PCP clearance. Inclusion/Exclusion criteria are presented in Table 2.

Table 2: Participant Eligibility Criteria for an 18-month Physical Activity Intervention in Adolescents with Intellectual and Developmental Disabilities

Inclusion	
Residential Status:	Living at home with a parent or guardian who is willing to participate in the intervention, with no plans to change this living situation and/or to leave the study area in the next 18 mos.
Age:	10-21 years
Diagnosis:	Mild to moderate IDD as verified by their PCP
Ambulatory:	Must be able to participate in physical activity.
Health status:	Must provide physician clearance to participate.
Communication:	Sufficient functional ability to understand directions, communicate preferences, wants, and needs through spoken language
Internet:	Internet access in the home
Exclusion	
Parent health concerns:	If the parent who will participate in the intervention with the participant has a serious medical risk, such as cancer, recent cardiac event, i.e., heart attack, stroke, angioplasty, or cannot participate in physical activity.

Pregnancy:	Pregnancy during the previous 6 mos., currently lactating or planned pregnancy in the following 24 mos. Participants who become pregnant will be removed from the study and referred to appropriate agencies for consultation.
-------------------	--

Recruitment Procedures/Randomization. Organizations and community agencies serving individuals with IDD will be mailed/mailed an information brochure that describes the project. Additionally, we will use email list serves and media advertising (print, radio, internet) to target families living in the recruitment area. Potential participants will be asked to contact a member of the study team to obtain details about the program and complete the initial eligibility screening. Remote video chat sessions (Zoom) will be scheduled with interested participants and their parent to describe the project in detail, answer questions, verify eligibility, and to obtain parent consent and adolescent assent. Study staff will set up a virtual Zoom meeting that allows for remote video chat. Prior to the consent meeting families will be emailed a link for a KUMC REDCap survey they will contain the consent and assent documents. Additionally, Study staff will “share screen” the consent document and walk through each section, noting questions that arise, and answer these questions fully. Participants and adolescents will sign the consent/assent documents on the REDCap survey. Study staff will then print and provide the participant with a full-signed consent form for their records at the baseline testing meeting.

Adolescents age 18 and over, who are their own legal guardian, will sign their own consent. Project staff will fax/email a form to the potential participant’s PCP, which describes the eligibility criteria, study requirements, and request for clearance for participation. Parents of adolescents found to be ineligible will be provided with written materials describing available resources for assisting their adolescent with increasing PA. Cohorts of ~10-20 adolescent/parent dyads will be recruited and computer randomized. Adolescents will be stratified by sex and the presence or absence of DS, and sequentially randomized by the study statistician with equal allocation to the AO or A+P arms.

Intervention Components

The intervention components for the AO and A+P arms are identical with the exception of the parental involvement component.

MVPA recommendations

Current US guidelines recommend a minimum of 60 min. of MVPA each day for children/adolescents with or without disabilities ²⁵. However, as described the limited available data suggest that few adolescents with IDD currently meet this recommendation ^{4, 26}. Therefore, the recommended daily MVPA, which will be identical for both groups, will progress from ~15 min./d during wk. 1, and gradually increase 10 min./d every 2 wks. during the active intervention to ~ 60 min./d at wk. 11, and remain at 60 min./d through mo. 18.

PA Self-Monitoring.

Participants in both arms will be asked to wear a Fitbit Charge 3TM (35.5 mm x 28 mm) activity tracker on their non-dominant wrist over the duration of the 18-mo. trial. Real-time data from the Fitbit is automatically transferred, via the web, to cloud storage maintained by Small Steps Labs LLC (Fitabase, San Diego, CA). Immediate participant feedback via a graphic display of daily steps, minutes of sedentary time, time spent in light, moderate and vigorous PA, and heart rate relative to pre-set goals will be available on the iPad. This data, accessible to health coaches, will be used *only* to provide motivation and feedback during intervention sessions. Outcome data for MVPA and sedentary time will be assessed by accelerometer. Participants will be reminded to wear and charge the Fitbit during group exercise sessions, and will receive automatic reminder messages via the iPad using the iCal app.

Introduction to Materials

After each participant’s baseline testing appointment (described in detail below), a member of the study team will outline study requirements and distribute all equipment, iPads, Fitbits, resistance bands, etc. The health coach will describe and demonstrate the ZoomTM software and the Fitbit, and will allow time for practice and questions.

Zoom Orientation

Each cohort of adolescents and parents in both intervention arms will be asked to attend an orientation session (~30 min.) led by their health coach. These sessions will be conducted on a Zoom conference call one week before the start of the intervention. This meeting is designed to establish rapport between the health coach and participants, and between participants themselves, prior to initiating the group video conference exercise sessions. Additionally, basic stretching exercises, the use of the resistance bands, and simple dance movements will be demonstrated and practiced.

Remote Group Physical Activity Sessions

Schedule. Group exercise sessions will be scheduled between 4 and 8 p.m., on 3 days/wk. from baseline to 6 mos. and 1 day/wk. during mos. 7-12. Participants in each cohort will be offered the choice between 2 session times each day. This meeting frequency and time were selected based on the preferences of parents of adolescents with IDD that participated in our pilot trial²⁷. Prompts reminding participants in both intervention groups of upcoming sessions will be sent via the iPad.

Delivery. Group exercise sessions will be delivered using an iPad tablet computer provided to all participants. The iPad will be pre-loaded with video-conferencing software (ZoomTM) which allows participation by multiple users. Participants will be provided with an iPad/HDMI adaptor, which allows video conference sessions to be displayed on a larger TV screen, if desired. Tutorials describing trouble shooting for common technical problems, e.g., internet connectivity etc., will be loaded on the iPad. Participants with technical issues during the intervention can also contact research staff by phone or email. Access to non-study related materials, e.g., web browsing, app store etc., will be blocked on all iPads until completion of the maintenance intervention (12 mos.). The iPads for both groups will also be pre-loaded with the Fitbit, Zoom, Dropbox, and Rooster Money applications.

Content. Each session will include a warm-up (~5 min.), moderate-to-vigorous intensity aerobic and resistance exercise (~30 min.), and cool-down/stretching (~5 min.). The resistance exercise component may be especially relevant for adolescents with DS who have reduced muscle strength compared with adolescents with other forms of IDD, as well as their typically developing peers⁹. All exercise sessions will be conducted by a health coach experienced in working with adolescents with IDD. The aerobic/resistance exercises, accompanied by music, will include walking/jogging in place, dancing, imitating animal movements, vertical/horizontal jumps, squats, and Thera-Band exercises for major muscle groups. Activities will be modified for participants having difficulty with specific movements. The intensity of the initial sessions will be light-to-moderate, with intensity increasing to moderate-to-vigorous at ~ 6 weeks. During each session, health coaches will encourage interactions between participants in support of their peer's efforts to increase MVPA, and provide participant feedback relative to their level of weekly MVPA as assessed by the Fitbit. As the intervention progresses, adolescent participants will be asked to volunteer to create and lead the group in a brief (3-5 min.) exercise bout. Adolescents will also be encouraged to interact with each other by performing activities such as tossing an imaginary ball to other participants, or challenging other participants to complete a skill such as 10 hops on one leg etc. All group sessions will be video recorded, and will be available on a Dropbox folder on the iPad for use by participants and/or parents across the 18-mo. trial.

Homework assignments

Adolescents who participate in all 3 weekly exercise sessions will have the potential to accumulate ~90 min. of MVPA/wk. (~13 min./d). Thus, MVPA outside these sessions will be required to meet weekly recommendations. Health coaches will provide weekly challenges in the form of meeting a goal for increased steps, trying a new activity, or creating and performing their own exercise routine etc. Scheduled group sessions will be reduced to 1/wk. during mos. 7-12, thus the volume of MVPA to be completed outside the group session, i.e., "homework" will increase to meet the recommended daily MVPA. Participants will be provided Dropbox access to previous exercise sessions they can complete on their own to meet weekly MVPA goals, if desired. Information regarding increasing PA, available from the National Center on Health, Physical Activity and Disability (NCHPAD) and the Special Olympic athletes home training guide, and similar material appropriate for parents, will also be loaded on the iPads of both intervention arms.

Parental Involvement

AO Arm. One parent/guardian will be asked to attend the orientation session, monitor MVPA across the intervention, and complete survey instruments at baseline, 6, 12, and 18 mos. (See assessments). By design, parental involvement in the AO group will be limited to reminder contacts (phone/text/email) from the health coach if their adolescent misses 2 consecutive exercise sessions. Contact attempts will be limited to 3 for each occurrence.

A+P Arm. One parent/guardian will be asked to attend the orientation session, monitor MVPA across the intervention, and complete survey instruments at baseline, 6, 12, and 18 mos. In addition that parent will be asked to participate in the group video exercise sessions, and attend 30-min. education/support sessions with their adolescent (1 session/mo., 0-12 mos.) delivered remotely on the iPad using FaceTime™. These sessions, led by the health coach, will be designed to educate and support parents in assisting their adolescent with meeting their 300 min./wk. goal for MVPA, and to assist parents with meeting their own weekly MVPA goal (150 min./wk.)²⁵. Each session will include a review of PA self-monitoring data, goal setting, strategies to increase and support MVPA, and discussion of a topic relevant to MVPA. Topics will include the importance of MVPA for health and function, how to include MVPA in the daily schedule, how to reduce barriers to PA, appropriate types of activity, creating a safe environment for PA, alternative activities for inclement weather, importance of hydration, etc. Session outlines and materials will be preloaded on the iPad where they can be accessed by adolescents/parents at any time. We will also create a private Facebook page for parents of adolescents in the A+P arm. Health coaches will post weekly helpful tips for adolescents/parents relative to increasing their MVPA, and provide information on community events and resources relative to PA (e.g., walk/running events, recreation center activities, etc.). Parents will also be encouraged to exchange information regarding opportunities for PA in their area, form support or activity groups, and post questions for the health coach to be answered during education/support sessions, etc.

Participant Incentives

Participants will be able to earn stars which can later be exchanged for money. Participants will be able to earn up to 2 stars each week, one for completing self-monitoring of PA on 5 of 7 days of that week, and one for attending 2 of the 3 scheduled exercise sessions during mos. 0-6 or the one session scheduled session during mos. 7-12. The allowance iPad app, Rooster Money (Rooster Money LLC, London, England), will be used to distribute stars to participants. Participants will get a notification on their iPad every time they receive a star as well as a note for what goal they achieved to get the star, and how many stars they currently have. Participants will receive \$10 each time they obtain 10 stars. Additionally, adolescents and parents will both receive \$50 for completion of each of the 4 outcome assessments. As an additional incentive, participants will be allowed to keep the iPad and the Fitbit on completion of the active intervention (12 mos.).

Outcome Assessments

With the exception of our primary outcome, MVPA, all outcomes will be assessed at either our Lawrence, or Kansas City, KS laboratories, based on participant preference at 0, 6, 12 and 18 mos. These assessments will be completed by trained staff blinded to intervention conditions. Staff will receive refresher training and complete reliability assessments for all physical measures 2-3 times/yr.

MVPA

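### The 60 min/d attainment outcome is an adolescent's average in the aims but a per-day yes/no in the analysis; separately, the adolescent goal is 300 min/wk in some sections and 60 min/d in others

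*Combined protocol and SAP*

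**What the plan says.** **Attainment outcome.** Among the Secondary aims is a comparison of the percentage of adolescents whose MVPA averages 60 min/d, over 18 months. The Secondary Aim analysis section says this percentage will be compared longitudinally with a generalized mixed model for repeated binary data, and defines the binary variable separately for each day observed. MVPA is recorded by accelerometer for 7 days at months 0, 3, 6, 9, 12, 15 and 18.

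**Behavioural goal.** Five places bear on what adolescents are asked to do:

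- Opening summary, both arms: homework is set "to reach a target of 300 min. of MVPA/wk".
- Overview of study design, both arms: homework and remote sessions together should "help them achieve a target of 300 min. of MVPA/wk".
- Parental Involvement, A+P Arm: education/support sessions ("1 session/mo., 0-12 mos") are for "assisting their adolescent with meeting their 300 min./wk. goal for MVPA".
- Table 1, both arms: 60 min/d.
- MVPA recommendations, both arms: national guidelines "recommend a minimum of 60 min. of MVPA each day". The trial's recommendation starts at about 15 min/d, rises by 10 min/d every two weeks to about 60 min/d at week 11, "and remain at 60 min./d through mo. 18".

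The Homework assignments section refers both to weekly recommendations and to a daily one, without giving minutes for either, so it does not settle which applies.

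**The concern.** On the first point, the declared outcome and the planned model have different units. The aim counts adolescents, each classified by an average. The model counts days, each classified alone. A statistician following the analysis section exactly would produce a result that does not answer the aim. If both definitions remain in the document, the choice between them could also be made after the data are seen.

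On the second point, the same adolescents are given two numerical goals. Coaches use a goal to set homework, to review self-monitoring data and to give feedback, and the tracker display shows activity and "heart rate relative to pre-set goals will be available on the iPad". An adolescent doing 300 min/wk has succeeded by one section and fallen short by another, and a team repeating the intervention could not tell which goal had been delivered.

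**Working it through.** **1. Attainment: do the two definitions agree?**

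Two constructed weeks show that they need not:

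| Week (min on each day) | Days reaching 60 | Mean, min/d | Averages 60? |
|---|---|---|---|
| 60, 60, 60, 60, 60, 0, 0 | 5 of 7 | 300/7 = 42.9 | No |
| 150, 150, 40, 40, 40, 0, 0 | 2 of 7 | 420/7 = 60.0 | Yes |

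The week with more successful days fails the aim's criterion, and the week with fewer meets it. This needs no distributional assumption.

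**2. How far apart could the percentages be? (illustration only)**

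Assume normally distributed daily MVPA with mean m, SD s and correlation r between days of the same week. Then:

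- P(day ≥ 60) = 1 − Φ((60 − m)/s)
- SD of the 7-day mean = s·√(r + (1 − r)/7)
- P(mean ≥ 60) = 1 − Φ((60 − m)/SD of the 7-day mean)

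Inputs: s = 15, 20 or 28.6, and r = 0.25, 0.5 or 0.7. The upper s is 35/√(2 × (1 − 0.25)) = 28.6, which reads the Power section's 35 min/d as the SD of a change and borrows its correlation of 0.25. All other values of s and r are assumed. Means: 23 min/d is the accelerometer level the Rationale reports from the team's earlier trial; 43 is 300/7 rounded; 60 and 65 are assumed.

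| Mean, min/d | Days ≥ 60 | Adolescents averaging ≥ 60 | Days minus adolescents, points |
|---|---|---|---|
| 23 | 0.7 to 9.8% | 0.0 to 6.7% | 0.5 to 8.3 |
| 43 | 12.9 to 27.6% | 2.9 to 24.5% | about 3 to 12 |
| 60 | 50% | 50% | 0 |
| 65 | 56.9 to 63.1% | 58.0 to 71.2% | −1.1 to −8.1 |

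Worked cell: m = 43, s = 20, r = 0.25. P(day) = 1 − Φ(17/20) = 19.8%. SD of the mean = 20 × √0.357 = 11.95. P(mean) = 1 − Φ(17/11.95) = 7.7%.

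The difference varies in size and changes sign above 60, so no single figure describes it.

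**3. Observations available.** Per-day: up to 7 days × 7 assessments = 49 binary values per adolescent. Average-based: up to 7.

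**4. Goal: converting to one unit.**

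The protocol's own conversions use a 7-day week. Homework assignments: 90/7 = 12.9, given as about 13 min/d. Power: 10 × 7 = 70 min/wk, as stated. On that basis:

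- 60 min/d = 60 × 7 = 420 min/wk
- 300 min/wk = 300/7 = 42.9 min/d
- Gap = 420 − 300 = 120 min/wk = 17.1 min/d

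Recommended weekly total along the ramp (daily figure × 7): week 1, 105; week 3, 175; week 5, 245; week 7, 315; week 9, 385; week 11, 420. It therefore passes 300 at about week 7, and the full gap applies from week 11. The daily recommendation runs to month 18, though the last six months are a "6 mos. no-contact follow-up".

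MVPA needed outside sessions, at about 30 min of MVPA per session (90/3):

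| Period | Goal 300 | Goal 420 |
|---|---|---|
| Months 0-6, 3 sessions/wk, full goal | 300 − 90 = 210 | 420 − 90 = 330 |
| Months 7-12, 1 session/wk | 300 − 30 = 270 | 420 − 30 = 390 |

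**The case against.** **On attainment.** The per-day outcome uses more of the data and sits closer to a guideline framed around each day. The average-based binary may be sparse: at 23 min/d the illustration puts only about 0 to 7% of adolescents at or above 60, and the Rationale cites a study in which no adolescent with IDD reached the recommended 60 min daily. With 57 per arm, a mixed model may not fit at some assessments. Rewording the aim would also remove the mismatch. The sparsity warning stands and shapes the fix. The rest is a case for keeping the per-day model alongside, not for letting it stand in for a percentage of adolescents it does not estimate.

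A reader might take the illustrated gaps as expected error in the trial's result. The documents do not support that: they give no within-week correlation or daily SD, and the Power section's f = 0.14 equals 10/(2 × 35), which treats 35 as a per-measurement SD, not the change SD assumed for the 28.6.

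**On the goal.** Since 300 is exactly 5 × 60, a five-day week may have been meant. That is plausible, but no section says so, and the guideline wording and the 7-day conversions point the other way. The documents do not settle it, so 300 cannot simply be called the error.

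Three stronger readings are tempting:

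- *Coaches cannot follow both numbers.* Too strong: the goals are nested, since 60 min every day also satisfies 300 min/wk. At 23 min/d (161 min/wk) both are far off.
- *The conflict is confined to weeks 11-52.* That is only the stretch where the full gap coincides with coaching; the ramp passes 300 earlier and the recommendation lasts to month 18.
- *The arms had different goals, because the coaching passage is A+P only.* The summary and overview give 300 min/wk for both arms, and Table 1 and the MVPA recommendations give 60 min/d for both.

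**Conclusion.** The attainment analysis is wrong as written: followed exactly, it estimates the chance that a monitored day reaches 60 min, not the percentage of adolescents averaging 60 min/d. That rests on the two sections' wording alone. The numerical size depends on the assumed mean, SD and correlation. Consequences are limited, because the secondary aims are stated not to be powered.

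The goal conflict is real and minor: 120 min/wk from week 11 if 60 min/d means every day, and none if five days a week was intended. It is a specification gap in a behavioural target common to both arms. Neither the goal nor the 60 min threshold enters the primary model or the power inputs (10 min/d, SD 35, r = 0.25, 21 measurements, 114 adolescents), so the primary analysis, the between-arm comparison and power are unaffected.

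**What to change.** **Attainment (main change).** In the Secondary Aim analysis, derive for each adolescent at months 0, 3, 6, 9, 12, 15 and 18 whether mean MVPA over the monitored days is at least 60 min/d, and state how many monitored days are required. Report that percentage by arm at each assessment. Compare arms with the generalized mixed model already planned, and name in advance a small-sample or penalised method for use if few adolescents reach 60. Keep the per-day model as supplementary.

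Cost: up to 7 rather than 49 binary values per adolescent, and possibly sparse events. No new data, visits or participants are needed.

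**Goal (minor change).** The sponsor should choose either 420 min/wk (60 min every day) or 60 min on 5 days a week (300 min/wk). The choice should then appear in the summary, the Overview of study design, Table 1, the MVPA recommendations and the A+P Arm text, and in the coach materials and device goals. If cohorts have already started, keep the goal they were given, so that earlier and later cohorts are not coached to different targets.

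Cost: wording and alignment of materials, provided the delivered goal is kept.
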